## 5.2. Secondary Efficacy Endpoint

Overall survival (OS) is defined as the time from the date of randomization to the date of death due to any cause. In the absence of confirmation of death, survival time will be censored at the last date the subject is known to be alive. Subjects lacking data beyond randomization will have their survival times censored at randomization.

The length of OS will be calculated as follows:

$$\text{OS (years)} = [\text{death date or last known alive date} - \text{randomization date} + 1] / 365.25.$$

## 5.3. Safety Endpoints

### Adverse Events

Assessment of adverse events will include: type, incidence, severity (graded by the National Cancer Institute [NCI] CTCAE, Version 4.03), timing, seriousness, and relatedness. Laboratory abnormalities will be recorded as an adverse event in accordance with the criteria in Section 8.4 of the protocol.

Baseline tumor-related signs and symptoms will be recorded as adverse events during the trial if they worsen in severity or increase in frequency.

---

|           |   |                 |           |
|-----------|---|-----------------|-----------|
| Document: | C:\Users\q764206\AppData\Local\Microsoft\Windows\Temporary Internet Files\Content.Outlook\GWW33WM3\ATLAS_SAPFinal v8.0_06MAR2018.docx |                 |           |
| Author:   | [name] (Updated [name]; [name]; [name], [name])  | Version Number: | Final 8.0 |
|           |   | Version Date:   | 06MAR2018 |

Template No: CS\_TP\_BS016 – Revision 2  
 Effective Date: 01Feb2010

Reference: CS\_WI\_BS005

**Statistical Analysis Plan**

---

**Laboratory Safety Assessments**

Hematology and blood chemistry will be drawn and urinalysis performed at the time points described in the Schedule of Activities and analyzed at local laboratories (Refer to Appendix 1 of the protocol). Investigators may have additional blood tests performed for the purpose of planning treatment administration, dose modification, or following adverse events, and these should be repeated as clinically needed. Prothrombin Time/International Normalizing Ratio (INR) should be performed to monitor subjects receiving concomitant warfarin or other anti-coagulants and when clinically indicated.

Thyroid Function Tests (Thyroid Stimulating Hormone [TSH], free T3 and free T4) should be performed for all subjects at baseline (Cycle 1 Day 1 pre-dose). Subsequently, TSH should be done at Cycle 1 Day 15, Cycle 2 Day 1, Cycle 3 Day 1, Cycle 4 Day 1, Cycle 5 Day 1, then every 8 weeks thereafter starting from Cycle 7 Day 1. TSH, free T3 and free T4 should be done on the next visit for any subject who has an elevated TSH in the previous visit. Hypothyroidism should be treated per standard medical practice to maintain euthyroid state with a normal TSH.

**Other Safety Assessments**

Other safety assessments to be assessed include: physical examinations, 12-lead electrocardiogram (ECG) (recorded at Screening only), height (recorded at Screening only), weight, vital signs (recorded at clinical study visits) and ECOG PS.

**5.4. Covariates**

**5.4.1. Stratification Factors**

As described in Section 3.2.2, randomization in this study is stratified by risk groups based on the AJCC TNM staging version 2010, ECOG PS and by country. Analyses for the primary and secondary endpoints as well as sensitivity analyses will be conducted based on analyses stratified by risk group only. Country will not be used as a stratification factor in analyses due to the limited number of subjects anticipated to be enrolled in some countries. Additional supportive analyses will not be stratified.

In the event a subject was randomized to the incorrect strata, the strata used for analysis will be obtained from the IWRS.

**6. Statistical Methods**

**6.1. General Methodology**

SAS version 9.2 or higher will be used in the statistical analysis.

The level of significance for the analysis of the primary variable at the interim and final analysis stages are described in Section 6.3. 95% confidence intervals (CIs) will be employed where appropriate

---

|           |   |                 |           |
|-----------|---|-----------------|-----------|
| Document: | C:\Users\q764206\AppData\Local\Microsoft\Windows\Temporary Internet Files\Content.Outlook\GWW33WM3\ATLAS_SAPFinal v8.0_06MAR2018.docx |                 |           |
| Author:   | [name] (Updated [name]; [name]; [name], [name])  | Version Number: | Final 8.0 |
|           |   | Version Date:   | 06MAR2018 |

Template No: CS\_TP\_BS016 – Revision 2  
 Effective Date: 01Feb2010

Reference: CS\_WI\_BS005

**Statistical Analysis Plan**

---

Data for subjects who failed screening will be listed. This may include demographics, inclusion/exclusion criteria responses and reason for screen failure.

**6.1.1. Analyses for Continuous Data**

For continuous data, the following summary statistics will be presented: n, mean, standard deviation (StD), median, minimum and maximum.

Mean and median values will be reported to one decimal place greater than the original data they were collected from while the StD will be reported to two decimal places greater than the original data. Minimum and maximum values will be reported with the same precision as they were collected.

**6.1.2. Analyses for Categorical Data**

For categorical variables, statistical summaries will include counts and absolute or relative percentages. The number of missing values will be presented where necessary.

Percentages will be reported to 1 decimal place. Percentages will be calculated using a denominator of all subjects in a specified population.

For by-visit analyses e.g. shift from baseline in toxicity grade of laboratory parameters only subjects with a measurement available will be included in the denominator for that visit.

**6.1.3. Analysis of Time-To-Event Endpoints**

Time-to-event endpoints will be summarized using the Kaplan-Meier method and displayed graphically when appropriate. Median event times and 2-sided 95% CI for each median will be provided based on the Brookmeyer-Crowley method.

Difference in time-to-event endpoints will be tested using a 2-sided stratified or unstratified log-rank test, where applicable. The stratified analysis will be performed as stated in Section 5.4.1.

Cox proportional hazards model will be used to estimate the hazard ratio and its 95% CI.

A parametric model will also be implemented as a sensitivity analysis of DFS.

**6.2. Handling of Dropouts or Missing Data**

---

|                 |   |                 |             |
|-----------------|---|-----------------|-------------|
| Document:       | C:\Users\q764206\AppData\Local\Microsoft\Windows\Temporary Internet Files\Content.Outlook\GWW33WM3\ATLAS_SAPFinal v8.0_06MAR2018.docx |                 |             |
| Author:         | [name] (Updated [name]; [name]; [name], [name])  | Version Number: | Final 8.0   |
|                 |   | Version Date:   | 06MAR2018   |
| Template No:    | CS_TP_BS016 – Revision 2  | Reference:      | CS_WI_BS005 |
| Effective Date: | 01Feb2010   |                 |             |

**Statistical Analysis Plan**

---

Subjects who discontinue study treatment will continue to be followed-up for DFS and OS until the time they have an event, or until the time of final analysis for DFS and OS. Subjects who withdraw from the study and are lost to follow-up will not be replaced. Surviving subjects without a DFS event and/or OS event at the time of the final analysis will have their DFS censored as described in Appendix A. All other missing data will be left as missing with the following exception as described in Section 6.2.1.

**6.2.1. Missing Data in Adverse Event Dates**

Missing dates in adverse events will be imputed as described below:

- For the start date, if the day of the month is missing, the 1st day of the month will be used to replace the missing date unless it is the month of the first dose. In that case, the start date will be imputed as the first dose date. If both day and month are missing, the 1st of January of the non-missing year will be used to replace the missing date unless the non-missing year is the same year as first dose in which case the start date will be imputed as the first dose date.
- For the stop date, if the day of the month is missing, the last day of the month will be used to replace the missing date. If both day and month are missing, December 31 of the non-missing year will be used to replace the missing date.

If the start date is missing for an adverse event, the adverse event is considered to be treatment-emergent.

**6.2.2. Missing Data in Safety Endpoints**

The percentage of subjects with an adverse event will be calculated using the number of as-treated subjects as the denominator. Therefore, no subjects in the as-treated population are excluded from adverse event displays. The denominator for summary tables for each laboratory parameter will be all subjects in the as-treated population with at least one evaluable cycle for that parameter. Different laboratory parameters may have different denominators, depending on the number of evaluable subjects for each parameter. An evaluable cycle is any cycle with at least one assessment of that parameter. Therefore, subjects with no assessments of a particular laboratory parameter are not included in the analysis of that parameter.

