- 8. **Hematology, Blood Chemistry, Urinalysis**: See Appendix 1 of the protocol for required tests. Hematology, chemistry and urinalysis will be done 2 weeks prior to starting treatment (screening). Results of the tests must be awaited before randomizing patients. Thus, days for test results should be taken into consideration. After the first cycle, the hematology, chemistry and urinalysis will be repeated at Day 1 of every cycle (4 weeks) until Cycle 5 Day1, then every 8 weeks thereafter starting from Cycle 7 Day 1. If urine protein is ≥2+ by semi-quantitative method (ie, dipstick) at screening or on study, then urine protein:urine creatinine ratio should be performed. PT/INR should be performed to monitor patients receiving concomitant warfarin or other anti-coagulants and when clinically indicated.
- 9. **Thyroid Function Tests**: Thyroid Function Tests (TSH, free T3 and free T4) should be performed for all patients at baseline (Cycle 1 Day 1 pre-dose). Subsequently, TSH should be done at Cycle 1 Day 15, Cycle 2 Day 1, Cycle 3 Day 1, Cycle 4 Day 1, Cycle 5 Day 1, then every 8 weeks thereafter starting from Cycle 7 Day 1. TSH, Free T3 and free T4 should be performed on the next visit for any patient who has elevated TSH. Hypothyroidism should be treated per standard medical practice to maintain euthyroid state with a normal TSH.
- 10. **Pregnancy Testing:** Patient of childbearing potential must have a negative pregnancy test within 14 days prior to the date of randomization and must be using appropriate birth control or practicing abstinence. Pregnancy tests may also be repeated as per request of IRB/IECs or if required by local regulations.
- 11. **12-lead electrocardiogram (ECG):** To determine the QTc interval at screening, the average of three consecutive 12-lead ECGs should be done. Screening ECG should be performed no more than 2 weeks prior to randomization. If the QTc interval is prolonged (>500 msec), the ECG should be re-read by a cardiologist at the site for confirmation. ECGs should be repeated as clinically indicated.
- 12. **ECOG Performance Status (ECOG PS):** Evaluation of ECOG PS at screening should reflect the patient condition just prior to nephrectomy. Baseline ECOG PS should be made prior to randomization and start of treatment. Follow-up assessments will be done at Day 1 of every cycle (4 weeks) until Cycle 5 Day1, then every 8 weeks thereafter starting from Cycle 7 Day 1.

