#### 5.3.4.3. Axitinib/Placebo Dose Reduction for Proteinuria

- If dipstick shows ≥2+ proteinuria, perform UPC. Dosing may continue while waiting for test results.
- If UPC < 2.0 is reported, continue dosing at the same dose level.

- If UPC ≥ 2.0 is reported, hold dosing and repeat UPC (interval at investigator discretion) until UPC is < 2.0. Restart axitinib/placebo at the same dose or one lower dose level at discretion of the investigator. Repeated UPC can be performed during treatment interruption at the site laboratory.
- If UPC  $\geq$  2 despite dose reduction to 1 mg BID, discontinue dosing.

Patients removed from treatment for intolerable toxicity should still be followed with regular tumor assessments until recurrence or occurrence of a secondary malignancy or start of new treatment, and for survival thereafter.

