**7.5.2. Clinical Laboratory Evaluation**

Laboratory tests to be performed, and timing of collection, are detailed in Section 7.2.2 of the protocol and include the following:

- Hematology: Hgb, white blood cell count (WBC), absolute neutrophil count (ANC), lymphocyte count and platelet count.

---

Document: C:\Users\q764206\AppData\Local\Microsoft\Windows\Temporary Internet Files\Content.Outlook\GWW33WM3\ATLAS\_SAPFinal v8.0\_06MAR2018.docx  
 Author: [name] (Updated [name]; [name]; [name], [name])      Version Number:      Final 8.0

Version Date: 06MAR2018

Template No: CS\_TP\_BS016 – Revision 2      Reference: CS\_WI\_BS005  
 Effective Date: 01Feb2010

Statistical Analysis Plan

---

- Chemistry: Total bilirubin, aspartate aminotransferase (AST), alanine aminotransferase (ALT), alkaline phosphatase, albumin, total protein, lactate dehydrogenase (LDH), sodium, potassium, chloride, calcium, phosphate, blood urea nitrogen (BUN)/Urea, creatinine, glucose.
- Urine dipstick for protein (subjects with  $\geq 2+$  protein will have urine protein creatinine [UPC] ratios).
- Pregnancy test, if applicable. Urine pregnancy test will be conducted at sites for females of childbearing potential only. If positive, then serum test should be conducted at central laboratories.
- Thyroid Function: TSH, free T3 and free T4

Baseline laboratory values will be selected from the date closest to but on or prior to the first dose (if there is more than one baseline evaluation).

Summary statistics for actual values and change from baseline will be presented for all planned time points for Hematology, Chemistry, Urinalysis and Thyroid function tests.

Shift from baseline to all post-baseline time points will be produced for urine protein.

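### Planned laboratory summaries of triggered tests (UPC, and free T3/T4 after baseline) would compare arms within subsets selected by a drug-affected result; the SAP needs a triggered-test rule

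*SAP*

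**What the plan says.** **Denominators.** SAP 6.2.2 sets the laboratory denominator as "all subjects in the as-treated population with at least one evaluable cycle for that parameter", adds that "An evaluable cycle is any cycle with at least one assessment of that parameter", and concludes: "Therefore, subjects with no assessments of a particular laboratory parameter are not included in the analysis of that parameter". For by-visit categorical tables, SAP 6.1.2 says that "only subjects with a measurement available will be included in the denominator for that visit". Neither section makes an exception for tests that another result triggers.

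**Planned output.** SAP 7.5.2 lists TSH, free T3 and free T4 as the thyroid function tests and states: "Summary statistics for actual values and change from baseline will be presented for all planned time points for Hematology, Chemistry, Urinalysis and Thyroid function tests". UPC appears there only in a parenthesis attached to the urine dipstick. The same section plans a shift table for urine protein, and a below/within/above-normal count for parameters that have no CTCAE grading. It says unscheduled results will only be listed.

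**When the tests are done.** Protocol Schedule of Assessments, footnote 8: "If urine protein is ≥2+ by semi-quantitative method (ie, dipstick) at screening or on study, then urine protein:urine creatinine ratio should be performed". Protocol 5.3.4.3 repeats the trigger: "If dipstick shows ≥2+ proteinuria, perform UPC". Footnote 9 has TSH, free T3 and free T4 measured in everyone at Cycle 1 Day 1 before dosing. After that only TSH is routine, and "Free T 3 and free T 4 should be performed on the next visit for any patient who has elevated TSH".

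**The concern.** Dropping subjects without a measurement is reasonable when everyone is scheduled for the test. For a triggered test, the absence of a result normally means that the parent test did not cross its threshold, so it carries information about the outcome. Proteinuria and thyroid dysfunction are adverse events of special interest in SAP 7.5.1.2, so the treatment can plausibly change who is tested. A tested-only table then conditions on a post-randomization outcome and loses the protection of randomization.

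Two features add to this:

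- **Change from baseline in UPC** can be computed only for subjects whose screening dipstick was already 2+ or more. Inclusion criterion 7 admits those subjects only if UPC is below 2.0. Subjects who first develop proteinuria on treatment have no baseline UPC.
- **Post-baseline free T3/T4** come at the visit after the high TSH, which can be 8 weeks later once visits are 8-weekly. The protocol says hypothyroidism should be treated, so the value may partly reflect replacement therapy.

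At stake is whether these particular tables can be read as arm comparisons, both in the final report and in the interim safety package that SAP 6.3 sends to the DMC.

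**Working it through.** The documents give no rate for dipstick ≥2+, for UPC ≥2.0 or for low free T4 in this trial, so there is no plan figure to reproduce. The check has two parts.

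**1. Which rule selects which test**

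- *UPC.* A subject who never has a 2+ dipstick has no UPC. Under SAP 6.2.2 that subject is outside the denominator of any UPC summary.
- *Free T3/T4.* Every subject should have a Cycle 1 Day 1 value. An evaluable cycle is any cycle with one assessment, so read literally SAP 6.2.2 removes nobody for these tests. The selection comes from the by-visit rule in 6.1.2, and from the actual-value and change-from-baseline summaries in 7.5.2, which can only use measured values. If evaluable cycle was meant to be post-baseline only, 6.2.2 would select as well. The SAP does not say.

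**2. What a tested-only denominator can do**

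Let t be the proportion triggered and c the proportion abnormal among those tested.

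- Tested-only percentage = c
- Percentage of all treated = t × c

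Take 350 per arm (about 700 randomized 1:1, SAP 3.1), and assume all are treated, all have the parent test and all who trigger are tested.

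*Main illustration, UPC ≥2.0.* t = 11% on axitinib is a stand-in: the all-grade proteinuria rate on axitinib in protocol Table 1. t = 2% on placebo is assumed. c = 1/3 in both arms is assumed.

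- Tested: 350 × 0.11 = 38.5 vs 350 × 0.02 = 7
- Tested-only: 33% vs 33%, ratio 1.0
- All treated: 0.11/3 = 3.7% vs 0.02/3 = 0.7%; difference 3.0 points, ratio 0.11/0.02 = 5.5
- Placebo trigger 1%: 3.7% vs 0.3%, difference 3.3 points
- Placebo trigger 5%: 3.7% vs 1.7%, difference 2.0 points

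*Other assumed inputs (axitinib vs placebo)*

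| Test | Triggered | Abnormal if tested | Tested-only ratio | All treated | Ratio |
|---|---|---|---|---|---|
| UPC | 10% vs 2.5% | 30% vs 30% | 1.00 | 3.0% vs 0.75% | 4 |
| UPC | 30% vs 10% | 30% vs 30% | 1.00 | 9.0% vs 3.0% | 3 |
| UPC | 20% vs 5% | 30% vs 40% | 0.75 | 6.0% vs 2.0% | 3 |
| UPC | 20% vs 5% | 40% vs 20% | 2.00 | 8.0% vs 1.0% | 8 |
| Free T4, post-baseline | 40% vs 10% | 25% vs 25% | 1.00 | 10% vs 2.5% | 4 |

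The third row reverses the direction. The fourth leaves the excess visible but smaller. In the last row, 10% vs 2.5% is also what the literal 6.2.2 denominator gives, because the Cycle 1 Day 1 test keeps every subject in.

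**The case against.** A reader might infer that the plan hides an axitinib excess in proteinuria or thyroid dysfunction. The documents do not support that, for four reasons.

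- **Other displays are not selected in this way.** Dipstick and TSH are scheduled for all subjects; the first has a planned shift table and the second planned summaries. Proteinuria and thyroid dysfunction are reported as adverse events over the whole as-treated population, with risk differences and ratios planned for the events of special interest. Under protocol 8.4, a result that needs further diagnostic testing or changes dosing is reportable as an adverse event, so many triggered findings should also appear there.
- **The 6.2.2 sentence does not reach free T3/T4**, because everyone has a Cycle 1 Day 1 value.
- **No table of UPC ≥2.0 by arm is promised.** A triggered UPC arguably has no planned time point, protocol Appendix 1 lists only urine protein under urinalysis, and unscheduled results are only listed.
- **Equal tested-only percentages follow from assuming equal conditional rates.** The 11% is an adverse-event rate in metastatic disease, not a dipstick rate. SAP 6.1.1 requires n for continuous summaries, so unequal numbers tested would be visible there, and SAP 7.5 plans no formal safety comparison.

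All four points stand, and they limit the issue to particular tables. They do not remove it. SAP 7.5.2 names free T3/T4 and calls for their change from baseline, so those columns will be conditional and unlabelled. For UPC, either a summary is produced on a selected denominator, or there is only a listing and no laboratory table shows how many subjects per arm reached the protocol's own 2.0 cut-off. The dipstick shift table does not show that, and TSH alone does not show high TSH with low free T4.

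The delay before free T4 and the absence of a low-TSH trigger are testing choices in the protocol. No denominator rule changes them.

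**Conclusion.** The point holds for specific laboratory outputs: post-baseline free T3/T4 summaries (through SAP 6.1.2 and 7.5.2) and any UPC summary (through SAP 6.2.2). These would compare arms within subsets defined by a post-randomization result that treatment can affect. In the illustrations, a 3- to 5.5-fold excess among all treated appears as no difference, or reversed at a ratio of 0.75. In another it remains visible as a ratio of 2. The trigger and conditional rates are all assumptions for this trial, so the figures show that masking is possible, not that it will occur or how large it would be.

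The safety report as a whole still carries the proteinuria and thyroid signals. Severity: minor. This is a cheap improvement that should be settled before unblinded safety tables are produced.

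**What to change.** Add a triggered-test rule to SAP 6.2.2 and 7.5.2 covering UPC and post-baseline free T3/T4:

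1. Show per arm the number triggered and the number tested. Triggered but untested subjects are the true missing data.
2. Over all as-treated subjects with at least one post-baseline parent test (dipstick or TSH), report the proportions with dipstick ≥2+, with UPC ≥2.0 after such a dipstick, and with high TSH followed by low free T4.
3. Count untriggered subjects as not meeting these composite criteria only. Do not count them as having normal free T4, which was not measured.
4. Drop the tested-only mean and change-from-baseline tables for these tests, or label them as conditional on triggering. Keep the listings.
5. State whether an evaluable cycle must be post-baseline.

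Cost: SAP wording and a little table programming, using data already collected. The downside is that the mean-change tables for UPC, free T3 and free T4 are lost or relabelled.

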**6.3. Interim Analysis and Data Monitoring Check spending function**

A single interim analysis (IA) is planned for this study. O’Brien – Fleming type stopping boundaries based on the Lan-DeMets spending function will be applied to the primary endpoint DFS (as assessed by IRC). Futility criteria are not used to calculate the nominal alphas (non-

---

|           |   |                 |           |
|-----------|---|-----------------|-----------|
| Document: | C:\Users\q764206\AppData\Local\Microsoft\Windows\Temporary Internet Files\Content.Outlook\GWW33WM3\ATLAS_SAPFinal v8.0_06MAR2018.docx |                 |           |
| Author:   | [name] (Updated [name]; [name]; [name], [name])  | Version Number: | Final 8.0 |
|           |   | Version Date:   | 06MAR2018 |

Template No: CS\_TP\_BS016 – Revision 2  
 Effective Date: 01Feb2010

Reference: CS\_WI\_BS005

